4.17. Exposure and drug adherence

Exposure and extent of exposure as well as data on drug adherence/compliance will be presented in tabular form with descriptive statistics calculated as described in section 4.2.6.

4.18. Additional analyses

After conclusion of main analyses, additional statistical analysis will be performed. Details of these analyses are beyond the scope of this document but a broad scope is described below.

Primary and secondary endpoints will be analyzed for subgroups based on two additional age categories: 18-37 vs 38-56 years old.

As part of additional analysis several endpoints will be considered:

- Change from Baseline in Disease Activity Score DAS28-ESR at Week 12
- Proportion of subjects based on category of response in change of DAS28-CRP score on week 12 (see section 4.2.8)
- Relationship between DAS28-CRP remission and ACR criteria.

Primary and secondary endpoints will be also analyzed in context of RA duration (<5 years vs. \geq 5 years).

All additional analysis will be performed on ITT population without imputation. If results are scientifically encouraging, PP and ITT with imputations will be also used to generate analyses.

5. Software and statistical programming

R programming will be performed according to Biostat standards as defined in PS11/2018 SOP “Data analysis” and related work instructions. The statistical analysis will be performed using the R statistical software package (Version 4.0.3 or later). Calculation of pharmacokinetic parameters will be performed in Phoenix WinNonlin 8.4 or later, except C_{trough} , accumulation ratio for $AUC_{(0-6h)}$, and accumulation ratio for C_{max} . PK parameters C_{trough} , accumulation ratio for AUC_{tau} , and accumulation ratio for C_{max} calculations and all other than PK parameters calculation analyzes will be performed using R statistical software package (Version 4.1.3 or later), based on the results obtained from the PK parameters calculations performed using WinNonlin or raw data on analyte concentrations. Pharmacodynamic analyses will be performed in R statistical software package (Version 4.1.3 or later).

6. References

Chow, S.C. and Liu, J.P. 2000. Design and Analysis of Bioavailability and Bioequivalence Studies, Second Edition, Revised and Expanded. Marcel Dekker, New York.

ICH Topic E9: Statistical Principles for Clinical Trials, 5 February 1998, adopted by CPMP, March 1998, issued as CPMP/ICH/363/96

ICH Topic E10: Choice of Control Group and Related Issues in Clinical Trials, adopted by CPMP, 20 July 2000, issued as CPMP/ICH/364/96

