3.2. Definition of subgroups

Analysis of primary and secondary endpoints will be provided for ITT and PP populations by the following subgroups:

- Age (<57 years old vs ≥57 years old)

- Sex (male vs. female)
- Disease severity based on DAS28-CRP score at baseline (moderate vs. high).

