3.5. Timing of analyses

Data analysis will be performed after all the data will be completed, verified, whole database will be locked and unblinded, with the exception of PK and PD analyses, which will be analysed after the end of the treatment period of all study participants.

4. Statistical analysis specification

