4.6. Handling of withdrawals, missing values and outliers

For the main analyses performed using the ITT and PP populations, data will be analyzed as observed during the study, no imputation rule will be applied.

A sensitivity analysis will be conducted for primary and secondary efficacy endpoints, whereby missing data are imputed using last observation carried forward method (LOCF) for continuous endpoints and non-responder imputation (NRI) method for binary endpoints.

In pharmacokinetic analyses, missing drug concentration data (no value, not available, NA) will be omitted from PK calculations. Drug concentration data below LLOQ will be treated in pharmacokinetic analysis as follows:

- If the concentration below LLOQ is recorded after the last measurable concentration in the dosing interval, then it is omitted from area calculations and elimination phase analysis.
- In other cases the concentration below LLOQ concentration value is set to zero.
- If an entire concentration-time profile below LLOQ, the profile will be excluded from the PK analysis.

For descriptive statistics of drug concentrations and calculation of PK parameters obtained directly from the observed concentrations (including C_{max} , $C_{min,ss}$, $C_{max,ss}$, C_{trough}) values below LLOQ will be set to zero.

A worst-case scenario will be used in the estimation of partial dates such as adverse events, medical history, rheumatoid arthritis history, smoking history or concomitant medications. That is, for an incomplete start date the first day of the month or the first month of the year will be used. For an incomplete stop date the last day of the month or the last month of the year will be used. If an estimated start date of event is earlier than the date of day 1 or the start date is completely missing, day 1 will be used, unless documented data does not allow for this interpretation.

If start date of smoking is completely missing, it will be replaced with the date of 18th birthday. For completely missing stop date of smoking, date when informed consent was signed will be used.

Whenever estimated dates will be calculated, the incomplete date will be listed and the study day will be calculated using the estimated date. These study days will be flagged as estimated in listings with a star (*) symbol.

For other situations regarding missing data not mentioned in this document, missing data will generally not be replaced or imputed.

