4.11. Efficacy analyses

Unless otherwise specified all efficacy analyses will be performed on ITT data with sensitivity analyses performed on PP population and ITT population with data imputed using methods described in section 4.6. In addition, efficacy analyses will be performed in subgroups defined in section 3.2.

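### SAP 4.18 adds the per-protocol and imputed versions of its exploratory analyses only when the first, unblinded results look encouraging, so their robustness is checked and displayed unevenly

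*SAP*

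**What the plan says.** SAP 4.18 lists further work: two extra age strata (18-37 and 38-56 years), RA duration below versus at least 5 years, change in DAS28-ESR at Week 12, DAS28-CRP response categories, and the relation between DAS28-CRP remission and the ACR criteria.

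- **Base version, without condition:** "All additional analysis will be performed on ITT population without imputation".
- **Supporting versions, with condition:** "If results are scientifically encouraging, PP and ITT with imputations will be also used to generate analyses".
- **Timing:** "After conclusion of main analyses, additional statistical analysis will be performed". On the state of the data at analysis, SAP 3.5 has: "whole database will be locked and unblinded, with the exception of PK and PD analyses".
- **Detail:** "Details of these analyses are beyond the scope of this document but a broad scope is described below".

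The rest of the SAP treats the same supporting versions differently. Section 4.11 sets the default: "Unless otherwise specified all efficacy analyses will be performed on ITT data with sensitivity analyses performed on PP population and ITT population with data imputed". Sections 4.11.1 and 4.11.2 repeat it for the primary and secondary endpoints. For the main subgroups (age at 57, sex, baseline severity), section 3.2 says: "Analysis of primary and secondary endpoints will be provided for ITT and PP populations by the following subgroups". None of these depends on how the results turn out.

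**The concern.** The analysis sets for a group of exploratory outputs are chosen after seeing those outputs. The SAP writes this down as a rule, so it is not a detail left for later. It gives no threshold for an encouraging result and does not say who decides.

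Two things follow. First, a reader of the report may see some findings backed by three agreeing tables and others by one, and take the difference as a difference in strength of evidence. Part of it would come only from the trigger, because the three tables re-analyse largely the same patients. Second, sensitivity analysis is useful in both directions. A flat as-observed result can also be a product of who dropped out, and under this rule that is not examined. The plan itself allows for about 16% dropout (SAP 2.3), which is 25 - 21 = 4 patients per arm.

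At stake is how much weight the exploratory findings of 4.18 appear to carry. The trial's main conclusion is not at stake.

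**Working it through.** The plan states no figure on this point that could be reproduced. The check is a comparison of the rules, then a count.

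**1. Rules compared**

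| Analyses | Source | ITT as observed | PP | Imputed ITT |
|---|---|---|---|---|
| Primary and secondary endpoints | SAP 4.6, 4.11, 4.11.1, 4.11.2 | always | always | always |
| Subgroups by age at 57, sex, severity | SAP 3.2 | always | always | not named in 3.2 |
| Additional analyses | SAP 4.18 | always | only if encouraging | only if encouraging |

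The default in 4.11 admits exceptions, and 4.18 is one. The documents therefore do not contradict each other; 4.18 departs from the SAP's own practice.

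**2. Versions per analysis**

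SAP 4.6 gives one imputation method per type of endpoint: missing values are "imputed using last observation carried forward method (LOCF) for continuous endpoints and non-responder imputation (NRI) method for binary endpoints". So:

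- encouraging: 1 (ITT as observed) + 1 (PP) + 1 (ITT imputed) = 3 versions;
- otherwise: 1 version.

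**3. Effect on what is displayed**

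Let q be the fraction of first results judged encouraging. The documents give no value and no criterion, so q is an assumption and a range is shown. It is also assumed that the trigger is applied to each result separately.

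- Equal treatment: encouraging share of displayed results = q.
- Rule in 4.18: share = 3q / (3q + 1 - q) = 3q / (1 + 2q).

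| q (assumed) | Equal treatment | Rule in 4.18 |
|---|---|---|
| 0.025 | 2.5% | 0.075/1.05 = 7.1% |
| 0.05 | 5% | 0.15/1.10 = 13.6% |
| 0.10 | 10% | 0.30/1.20 = 25.0% |
| 0.20 | 20% | 0.60/1.40 = 42.9% |
| 0.50 | 50% | 1.50/2.00 = 75.0% |

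The odds go from q/(1 - q) to 3q/(1 - q), a factor of 3 for any q. This measures display only. It is not an error rate.

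**4. After the fix**

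With three versions for every analysis, or one for every analysis, the share returns to q.

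**The case against.** The strongest case on the other side has five parts.

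- **Nothing is hidden.** Every additional analysis is run on ITT as observed, whatever its direction. This stands. A reader might infer selective reporting from the conditional sentence, but the documents do not support that: only supplementary versions depend on the result.
- **The material is exploratory.** The additional analyses follow the main ones, and Protocol section 11 leaves other endpoints to be analysed as appropriate. This stands, and it limits the importance of the point. Section 11 also sends the details to the SAP, however, and 4.18 defers them again.
- **Encouraging need not mean favourable to CPL409116.** The term is undefined, and the remission-versus-ACR analysis has no favourable treatment direction. The sentence can also be read collectively: if the additional results as a whole encourage, all of them get the extra versions. On that reading the three-to-one imbalance between findings disappears, although the decision to check sensitivity would still depend on the results. This stands as a limit. The result-by-result reading is the natural one, but it is a reading.
- **Extra versions can weaken a finding.** PP and LOCF or NRI re-analyses are stress tests and may overturn an encouraging result. True, but a stress test applied to only some results does not show robustness evenly.
- **Dropout handling is examined elsewhere.** Imputed analyses of the primary and secondary endpoints are planned for the whole trial. This helps in part. It does not cover DAS28-ESR, the response categories, or the extra age and RA-duration subgroups.

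A reader might also be tempted to size the problem by counting contrasts at the 5% level and expecting a number of chance findings. That would measure multiplicity, not the conditional rule. Section 4.18 sets no p-value trigger, and the count would be the same after the fix.

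**Conclusion.** The point holds as a minor one. For the exploratory analyses of SAP 4.18, the supporting analysis sets are chosen by an undefined judgement on unblinded results. On the natural reading, encouraging results appear in three overlapping versions and others in one, and the sensitivity of the others to missing data goes unchecked. The size is a threefold increase in the odds that a displayed result is an encouraging one, assuming that the trigger works result by result.

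A reader might infer that the trial's efficacy conclusion, or its type I error on the primary endpoint, is affected. The documents do not support that. The primary and secondary endpoints have their PP and imputed versions without condition, and the section 3.2 subgroups have ITT and PP without condition. What is affected is the evenness of display and the apparent robustness of exploratory findings.

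**What to change.** Delete the conditional sentence in SAP 4.18. In its place, name one group of analysis sets that applies to every additional analysis whatever the results. Either choice removes the problem:

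- ITT as observed plus PP and imputed ITT, in line with 4.11; or
- ITT as observed only.

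State that all of the named versions will be reported and that the outputs are exploratory.

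The methods are already defined in the SAP: LOCF and NRI in 4.6, the PP set in 3.1. The first choice costs some additional tables; their number cannot be given, because 4.18 leaves the details open and the subgroup analyses span all primary and secondary endpoints. The second costs no extra tables.
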